4.1. Baseline Definition

For both the priming vaccination phase and booster vaccination phase, the baseline is defined as the last non-missing assessment prior to the first priming study vaccine administration. Both scheduled and unscheduled visits and assessments will be used in determining baseline. The change from baseline is calculated as the post-baseline value minus the baseline value.

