8.2. Analysis of Immunogenicity Primary and Secondary Endpoints

8.2.1. Analysis of primary and secondary immunogenicity endpoints

Total NAbS and BAbS titers will be summarized using descriptive statistics (number of subjects (n), median, minimum and maximum) by each time point in priming vaccination period (Baseline, Days 14, 28, 42, 56, 208) and booster vaccination period (Day 208, 236, Early Termination). Summaries of priming vaccination and booster vaccination periods based on their corresponding mITT and PP analysis sets will be presented separately using the applicable treatment groups (Table 4-1). For the analysis of booster mITT analysis set, summary tables with active boosters pooled (as presented in Table 4-1; e.g., A1, A2, B1, B2, etc.) will also be presented.

The following statistics will be provided in the summary tables and/or figures:

- Geometric mean titer (GMT) with corresponding 95% CI will be provided at each time point. The 95% CIs will be calculated based on the t-distribution of the log-transformed values then back transformed to the original scale for presentation. GMT level and corresponding 95% CI will be plotted at each timepoint in priming vaccination period for mITT analysis set. Plots of the reverse cumulative distribution curves also will be provided by treatment group and visit in priming vaccination period for mITT analysis set.
- Geometric mean fold rise (GMFR) with corresponding 95% CI will be provided at each post-baseline timepoint over baseline. The 95% CIs will be calculated based on the t-distribution of the log-transformed values then back transformed to the original scale for

presentation. GMFR and corresponding 95% CI will be plotted at each timepoint in priming vaccination period for mITT analysis set.

- The number and percentage of subjects with fold-rise ≥ 2 and fold-rise ≥ 4 from baseline (Seroconversion) at each post baseline time points will be tabulated with the 2-sided 95% CI using the Clopper Pearson method at each post-baseline timepoint.
- Seropositivity at a participant level is defined as any detectable antibody level above the lower limit of quantification (LLOQ) for the specific assay and antibody measured at timepoints after baseline. Seropositivity rates will be provided with 2-sided 95% CI using the Clopper-Pearson method at each post-baseline time point.

The definition of seroconversion/seropositivity may depend on assay-specific performance characteristics. The conventions are as follows:

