
- Seropositivity is defined as any detectable antibody level above the lower limit of quantification (LLOQ) for the specific assay and antibody measured.
- For the MesoScaleDiscovery nucleocapsid antibody test (VAC72_ECL_CoV-2_N), seroconversion will be assessed in 2 ways:
 - Defined as a 2- or 4-fold increase above baseline (pre-vaccination antibody levels).
 - Based on detection of an antibody level ≥ 5000 AU/mL, a threshold associated with evidence of SARS-CoV-2 clinical infection/viral exposure.
- For all other assays and antibodies, seroconversion will be defined as a 2- or 4-fold increase above baseline (pre-vaccination antibody levels).
- For seronegative individuals, one half of the value of the LLOQ will be calculated as the baseline antibody level

The LLOQs for each assay are shown below.

- VAC62_MN_CoV-2 (IU/mL): 7.8431372549
- VAC72_ECL_CoV-2_N (BAU/mL): 0.06372
- VAC72_ECL_CoV-2_RBD (BAU/mL): 0.5168

VAC72_ECL_CoV-2_S (BAU/mL): 0.20723 The GMT will be calculated using the following formula:

$$GMT = e^{\left\{ \frac{\sum_{i=1}^n \log_e(t_i)}{n} \right\}}$$

where t_1, t_2, \dots, t_n are observed immunogenicity titers for n participants.

The GMFR measures the changes in immunogenicity titers within participants. The GMFR will be calculated using the following formula:

$$GMFR = e^{\left\{ \frac{\sum_{i=1}^n \log_e \frac{v_{ij}}{v_{ik}}}{n} \right\}} = e^{\left\{ \frac{\sum_{i=1}^n (\log_e v_{ij} - \log_e v_{ik})}{n} \right\}}$$

where, for n participants, v_{ij} and v_{ik} are observed immunogenicity titers for participant i at time points j and $k=0$ (Baseline, Day 0).

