8.2.2. Supportive Analyses of Primary and Secondary Immunogenicity Endpoints

8.2.2.1. Supportive Analyses of Estimand 2

To assess the magnitudes of the differences between the treatment groups (ARCT-021 vs. Placebo) in SARS-CoV-2 neutralizing antibody (NAbs) and SARS-CoV-2 binding antibody (BAbs) endpoints, an analysis of covariance (ANCOVA) model will be fitted to the natural log transformed neutralizing antibody titers measured against SARS CoV 2 with terms for treatment group, age group (≥ 18 to < 56 and ≥ 56 years) (stratification factor at randomization) and natural log baseline titer by each post-vaccination immunogenicity visit. No imputation of missing data will be done.

The geometric least squares mean (GLSM) and corresponding 2-sided 95% CI for the antibody titers for each treatment group will be provided by visit. The GLSM and corresponding 95% CI results in log-transformed scale estimated from the model will be back-transformed to obtain these estimates in the original scale. Geometric mean ratio (GMR), estimated by the ratio of GLSM and the corresponding 2-sided 95% CI will be provided to assess the treatment difference between ARCT-021 group vs. placebo group at each visit.

ANCOVA analyses will be performed for the priming vaccination period on mITT analysis set only.

8.2.2.2. Supportive Analyses of Estimand 3

The common difference of seropositivity and seroconversion rates and 95% CIs between each vaccine dose group and the placebo will be estimated using the Miettinen-Nurminen method with age group (≥ 18 to < 56 and ≥ 56 years) as stratification factor for each time point.

Miettinen-Nurminen analyses will be performed for the priming vaccination period on mITT analysis set only.

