8.3.2. CMI Analysis

CMI responses will be evaluated for CMI subset using parametric flow cytometry for quantification and phenotyping and cytokine staining for TNF- α , IL-2, IFN- γ , IL-4, and IL-13. Blood sampling will be performed at Days 0, 14, 28, 42, 56, 208, 215, 236, and Early Termination in participants enrolled at centers identified with capabilities for isolation of peripheral blood mononuclear cells (PBMCs). CMI testing will not be performed on participants re-enrolling at Day 98-198 (i.e., placebo participants who re-enter the study to receive ARCT-021 priming vaccinations).

Descriptive statistics (N, mean, SD, min, Q1, median, Q3, max) will be provided for each visit including change from baseline at each timepoint, where CMI results are available for the priming vaccination period (mITT and PP analysis CMI subsets) and booster vaccination period (Booster mITT CMI subset). When summarizing the Early Termination visit, only include observations within the booster vaccination period post day 236. The following CMI responses will be summarized:

- CD4+ T-cell responses background subtracted (combined pools): IFN- γ , TNF- α , IL-2, IFN- γ + TNF- α +, IFN- γ + TNF- α + IL-2+
- CD8+ T-cell responses background subtracted (combined pools): IFN- γ , TNF- α , IL-2, IFN- γ + TNF- α +, IFN- γ + TNF- α + IL-2+

- Th1/Th2 CD4+ T-cell responses background subtracted (combined pools): IFN- γ , IL-4, IL-4+ IL-13+, IFN- γ + / IL4+ IL13+

Box plots will be provided for the following for priming vaccination period (mITT CMI subset): CD4+/CD8+ IFN γ , IL4+IL13+, IFN γ +/IL4+IL13+, Th1/Th2.

Analyses will be performed overall and by age group (younger adults (≥ 18 - < 56 years), older adults (≥ 56 years)) for priming vaccination period (mITT CMI subset).

Summary tables and figures will exclude any data points collected at or after the first occurrence of the following intercurrent events: death, missed second ARCT-021 (if applicable) dose, use of immune-modifying drugs, and study infection. Summary tables and figures will exclude all data from subjects with early (before Day 7), active or prior SARS-CoV-2 infection at first vaccination.

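### In ARCT-primed groups the booster-period fold-rises are measured only from Day 0, so no planned table shows who responded to the booster or gives a paired interval for the change from Day 208

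*SAP*

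**What the plan says.** SAP 4.1 states: "For both the priming vaccination phase and booster vaccination phase, the baseline is defined as the last non-missing assessment prior to the first priming" dose. SAP 8.2.1 carries this through. It plans that "Geometric mean fold rise (GMFR) with corresponding 95% CI will be provided at each post-baseline timepoint over baseline", and the GMFR formula takes titers at "time points j and $k=0$ (Baseline, Day 0"). For every assay other than nucleocapsid, "seroconversion will be defined as a 2- or 4-fold increase above baseline (pre-vaccination antibody levels"); nucleocapsid uses the same rule plus an absolute threshold. For CMI, SAP 8.3.2 plans descriptive statistics "provided for each visit including change from baseline at each timepoint, where CMI results are available", in the booster period as well as the priming period.

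The booster tables cover the "booster vaccination period (Day 208, 236, Early Termination"), so pre-booster values are displayed. SAP Table 4-1 includes H1, the ARCT-primed participants with a placebo booster or none.

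The model-based and stratified comparisons stop before the booster. SAP 8.2.2.1: "ANCOVA analyses will be performed for the priming vaccination period on mITT analysis set only". SAP 8.2.2.2: "Miettinen-Nurminen analyses will be performed for the priming vaccination period on mITT analysis set only".

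The booster objective (SAP 2.3) is exploratory. Its immunogenicity endpoint lists GMFR, seroconversion, GMC and GMT before and after the booster. The protocol synopsis describes GMFR generically as a later minus an earlier log value but names no pre-booster contrast, and SAP section 1 gives the SAP precedence.

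**The concern.** A participant primed with ARCT-021 may reach Day 208 well above the Day 0 value. A Day 236 fold-rise over Day 0 then multiplies what priming left behind by what the booster added. The seroconversion rate printed for E1, F1 or G1 does not say how many participants responded to the booster.

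Two quantities that describe the booster response directly are absent. One is the proportion with a 2- or 4-fold rise from the pre-booster value. The other is a confidence interval for Day 236/Day 208 that uses the pairing within participants. Neither can be derived from marginal summaries at Day 208 and Day 236, because both need the joint distribution of the two visits.

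A fold-rise rate near 100% at Day 208 would also have little room to move. Protocol 1.6 reports a 4-fold or greater spike response by the MSD binding assay in more than 90% of participants after single 5-µg doses, and every ARCT priming regimen contains at least one dose of 5.0 µg or more.

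**Working it through.** **Identity.** In the same participants, GMFR(236/0) = GMFR(208/0) × GMFR(236/208). With an inert booster the second factor is 1, and the Day 0 results at Day 236 repeat those at Day 208.

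**Inputs from the documents.** Log SD 1.2 (SAP 4.2); 4-fold spike rate above 90% after one 5-µg dose (Protocol 1.6), taken as 90%; 600 participants, three of four arms ARCT-primed, boosters 1:1:1:1 (SAP 3.1 and Table 3-1).

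**Assumptions.** Log-normal responses; the 1.2 used as the SD of log fold-rise over Day 0; a true 3-fold booster; fraction w of the priming fold-rise retained at Day 208; correlation ρ between log values at Day 208 and Day 236 of 0.5 or 0.8. The documents report neither w nor ρ.

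**Spike binding antibody, rate against Day 0.** A 90% 4-fold rate implies a median fold m = 4 × exp(1.2816 × 1.2) = 18.6. For booster multiplier b, the rate is Φ(ln(m·w·b/4)/1.2).

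| w | Day 208 rate, or Day 236 with inert booster | Day 236 rate, b = 3 | Gain |
|---|---|---|---|
| 100% | 90% | 99% | 9 points |
| 50% | 76% | 95% | 19 points |
| 25% | 55% | 85% | 30 points |
| 12.5% | 33% | 68% | 35 points |

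**Rate against Day 208.** The SD of the log change is 1.2 × √(2(1−ρ)), which is 1.2 at ρ = 0.5 and 0.759 at ρ = 0.8. The rate is 1 − Φ(ln(4/b)/SD).
- ρ = 0.5: 12.4% for an inert booster, 40.5% for b = 3, a gain of 28 points.
- ρ = 0.8: 3.4% and 35.2%, a gain of 32 points.

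These gains do not depend on w.

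**Sensitivity to the SD.** At SD 0.8 the Day 0 gains are 10, 30, 50 and 43 points, against 28 to 32 from Day 208. At SD 1.6 they are 7.6, 13.6, 20.4 and 25.5 points, against 24 to 30.

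**Neutralizing antibody.** Take Day 0 below the LLOQ (set to 7.843/2 = 3.92 IU/mL) and residual folds of 2, 4 and 8. The Day 236 4-fold rate against Day 0 is 28%, 50% and 72% for an inert booster, and 63%, 82% and 93% for a 3-fold booster: gains of 35, 32 and 21 points. Against Day 208 (simulated, values below LLOQ halved as in the SAP), the inert rate is 9–13% at ρ = 0.5 and 3–4% at ρ = 0.8. The 3-fold rates are 36–41% and 31–36%.

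**Interval width for Day 236/Day 208.** The 95% interval is the ratio divided and multiplied by a factor.
- From two separate GMTs: exp(t[2n−2] × 1.2 × √(2/n)).
- Paired: exp(t[n−1] × 1.2 × √(2(1−ρ))/√n).

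Planned numbers before attrition are 600 × 3/4 / 4 = 112.5 per primed active booster column (n = 112) and 225/4 = 56.25 in one age cohort (n = 56).

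| n | Separate GMTs | Paired, ρ = 0.5 | Paired, ρ = 0.8 |
|---|---|---|---|
| 112 | 1.37 | 1.25 | 1.15 |
| 56 | 1.57 | 1.38 | 1.23 |

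**The case against.** The strongest reply is that this asks for an extra summary and corrects no error. Day 0 is what Estimand 3 specifies, it is stated plainly, and it is the one reference that treats primed and unprimed groups alike. That stands: a reader might infer that SAP 4.1 contradicts the estimand, and it does not.

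A reader might also infer that the booster tables would hide an inert booster, or that E1, F1 and G1 must look alike. The documents support neither. Equal Day 208 and Day 236 rows, or a comparison with H1, would expose an inert booster. The ceiling applies to fold-rise rates, chiefly Wuhan spike binding antibody. GMT and GMFR have no such ceiling, and beta-strain assays are planned for the booster period.

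Nor is Day 208 the better reference throughout. For neutralizing antibody with a low residual, and for spike after heavy waning, Day 0 separates a 3-fold booster from an inert one at least as well.

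The booster question is posed against placebo, and a within-participant change has no control of its own: an inert booster still yields some 3–13% apparent 4-fold responders in the SD 1.2 scenarios. This also stands and shapes the fix. H1 must sit beside the active groups, bearing in mind that it pools placebo-boosted with unboosted participants.

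Participant listings (Protocol 7.6) should allow someone to compute the missing quantities, and early termination explains a trimmed plan. Neither puts the paired summaries in a planned table.

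**Conclusion.** The point holds as a minor, inexpensive improvement. In E1, F1, G1 and H1 the booster-period fold-rise results are cumulative. No planned table reports the post-booster responder rate or a paired interval for Day 236 against Day 208, although the endpoint is framed as responses before and after the booster.

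The loss of contrast in the spike 4-fold rate is material only if the priming response largely persists to Day 208: at SD 1.2, 9 or 19 points at 100% or 50% retention, against 28 to 32 with the pre-booster reference. At 25% retention the two references are about equal, and at 12.5% Day 0 does slightly better. Retention, correlation and the 3-fold effect are assumptions.

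The interval figures apply to primed active-booster columns only. A reader might take the SAP's minimum of 25 per booster group and obtain a wider gap. That number matches 75/3, one age cohort of placebo-primed participants, for whom the cumulative reading is not the issue. No primary or secondary result changes.

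**What to change.** In SAP 4.1, 8.2.1 and 8.3.2, define a second reference for the booster period: the last valid Day 208 visit value before the booster dose, or the Day 208 value if no booster was given, with no earlier value carried forward. For Day 236 and later, report against it:
- GMFR with paired t intervals;
- 2- and 4-fold rates with Clopper-Pearson intervals;
- CMI change.

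Show E1, F1, G1 and H1 side by side so that the active groups are read against H1. Keep all Day 0 results, labelled as the whole-regimen response, leave Estimands 2 and 3 unchanged, and label the new columns as additional descriptive summaries.

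The cost is one derived variable and extra table columns; Day 208 blood is already drawn before dosing. The tables become wider, and participants without a valid Day 208 sample drop out of the new columns.

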4.2. Sample Size

The sample size is based on clinical considerations to provide sufficient safety information for the analysis of the primary safety objective. With 75 participants randomly assigned to each priming vaccination dose group but with as few as 25 participants randomly assigned to individual booster vaccine groups Table 4-2 presents estimated probability to detect at least one adverse event at various incidence rates by possible sample size in this study. The estimated probability was calculated using a formula as below:

$$p = 1 - (1 - R)^N$$

where R = incidence rate and N = sample size.

If the incidence rate of an adverse event is 1%, the probability to detect one event in 75 vaccinated participants is 52.9%, and the probability of detecting one event in 25 vaccinated participants is 22.2%; however, this probability will be 95.1% in a sample size of 300 in each Age Cohort. See more details and scenarios in the table below.

Table 4-2 Probability to Detect at Least One Adverse Event by Incidence Rate of Event and Sample Size

Rate (%)	N=25	N=75	N=150	N=225	N=300
0.01	0.002497002	0.007472	0.014889	0.02225	0.029556
0.1	0.024702287	0.072291	0.139357	0.201574	0.259293
1.0	0.222178641	0.529413	0.778548	0.895788	0.950959
2.0	0.39653527	0.780236	0.951704	0.989386	0.997667
5.0	0.722610427	0.978656	>0.999	>0.999	>0.999
10.0	0.928210201	>0.999	>0.999	>0.999	>0.999

The study plans to randomize 75 participants to each Study Group within each Age Cohort. Assuming a geometric coefficient of variance (CoV) of 180% (SD of 1.2 on log_e scale), a sample size of 75:75 will provide a >99% power to detect 2-fold increase in antibody titers in ARCT-021 Study Groups versus placebo Study Groups. These power analyses were performed using PASS Version 15 software.

4.3. Study Blinding and Unblinding

The study is blinded to study site staff, participants, CRO staff and the sponsor up to Day 98 and again from Day 208 (administration of the booster) up to end of study. Between Day 98 and Day 208, a partial unblinding may occur as follows:

Between Day 98 and Day 198, certain site staff may become unblinded to some participants' treatment assignment to determine eligibility for re-enrollment ([Section 3.1](#)). At this point, these site staff will know whether the participants in question received active study vaccine or placebo during the initial priming vaccinations. The blinded CRO team will also be unblinded to who received active study vaccine or placebo for re-enrolled participants due to the ability to link the new re-enrolled participant ID with the previous participant ID in the database. At Day 208, participants are re-randomized to booster vaccination, which will be administered in a blinded fashion. The blinded site and CRO staff, the Sponsor team providing direct oversight of the study, and the SRC will remain blinded to individual participant vaccine assignments for the duration of the booster phase of the study. The identification of Sponsor team members and blinding status will be documented in an unblinding memo.

The study vaccines will be administered in an observer-blind fashion.

Each of the study vaccines will be prepared by an unblinded pharmacist and in accordance with the Pharmacy Manual.

Unblinded personnel (of limited number) will be assigned to vaccine accountability procedures and will prepare study vaccine for all participants. These personnel will have no study functions other than study vaccine management, documentation, accountability, preparation, and administration. They will not be involved in participant evaluations and will not reveal the identity of study vaccine to either the participant or the blinded study site personnel involved in the conduct of the study unless this information is necessary in the case of an emergency.

- Unblinded health care providers will administer the study vaccine. They will not be involved in assessments of any study endpoints.
- Unblinded site monitors, not involved in other aspects of monitoring, will be assigned as the study vaccine accountability monitors. They will have responsibilities to ensure that sites are following all proper study vaccine accountability, preparation, and administration procedures.
- An unblinded statistical and programming team will perform the pre-planned interim analyses.
- A DSMB will review the interim data to safeguard the interests of clinical study participants and to help ensure the integrity of the study. The DSMB will review unblinded statistical outputs and interim analysis results, provided by the unblinded statistician, and make recommendations to the Sponsor.

In order to maintain an observer-blind design, investigators, site staff, participants, and CRO staff with oversight of study conduct will remain blinded to vaccine assignments for the study

duration with the exception of the partial unblinding of required site staff, participants and CRO staff for re-enrollment purposes.

The plan to protect the blind and identification of unblinded Sponsor and PPD team members are documented in the following blinding plans:

- Arcturus Sponsor Blinding Plan - Unblinding Plan for Interim Analyses, V3.0, 15Mar2022
- PPD B&P Blinding Plan – ARCT-021-04_Biostatistics and Programming Blinding Plan_V2.0 dated 20Jul2021.

4.4. Study Phases and Analysis Sets

There are two study phases defined:

- Priming Vaccination Period: All timepoints up through Day 208 (prior to booster vaccination).
- Booster Vaccination Period: All timepoints from Day 208 through Early Termination.

The following analysis sets are defined for the priming vaccination period: Randomized, Intent-to-Treat, Modified Intent-to-Treat, Per-protocol, CMI Subset, Safety, and Reactogenicity. A Randomized set, Reactogenicity Set, Safety, Modified Intent-to-Treat, CMI Subset set are defined for the booster vaccination period.

4.4.1. Randomized Analysis Set

The Randomized analysis set consists of all participants who are randomized, regardless of the participant's study treatment status in the study. Participants will be analyzed according to the study treatment group to which they were randomized.

- Note: The Randomized analysis set for re-enrolled participants consists of all re-enrolled participants who were re-randomized, regardless of the participant's study treatment status in the study.

4.4.2. Intent-to-Treat Analysis Set

The Intent-to-Treat (ITT) analysis set includes all participants who receive at least 1 dose of priming study vaccine (ARCT-021 or placebo). Participants will be analyzed according to the vaccine to which the participant was randomly assigned.

- Note: The ITT analysis set for re-enrolled participants consists of all re-enrolled participants who receive at least 1 dose of study vaccine while as a re-enrolled participant.

